Subjects will be able to ask any questions about the study to study investigators, who will be available at the request of the subject. Subjects have the option to withdraw from the study at any time, and this is explicitly stated in the consent form and will be emphasized at the time consent is obtained. Subjects may also be discontinued prematurely if they experience a clinically significant adverse event as determined by the clinical staff, if the subject requests to be withdrawn from the study, or if there are other conditions for which, in the investigator's opinion, it is in the subject's best interest to be withdrawn from the study.

All serious and/or unexpected adverse events will be reported to the IRB within 24 hours. All other adverse events will be reported in an annual continuing review report. This is not an interventional study, so the clinical care of these subjects will not be altered in any way.

X. References

6. Reuber M, Elger CE (2003): Psychogenic nonepileptic seizures: review and update. *Epilepsy Behav* 4:205-216.
7. Benbadis SR, Allen Hauser W (2000): An estimate of the prevalence of psychogenic non-epileptic seizures. *Seizure* 9:280-281.

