As noted above, research into the neurobiology of FND is in its early stages. Improved biological understanding of this disorder at the interface of Neurology and Psychiatry would reduce stigma associated with this condition, and potentially identify neuroimaging biomarkers of prognosis and treatment response as has been done for other neuropsychiatric disorders including PTSD(27, 30). Understanding the neurobiological basis of FND may aid disease prevention, risk factor identification, and promote the development of more successful and cost effective therapeutic interventions. Indeed, there is evidence to suggest that the earlier FND is identified and treated, the greater the likelihood of curing the illness(58) and avoidance of subsequent disability. Furthermore, the development and recognition of a neuropsychiatric model of this definable condition will also offer translational clinical and research opportunities to the larger problem of psychosomatic disease.

Examining the neurobiology of FND will also facilitate a better understanding of the larger problem of psychosomatic illness that burdens our healthcare system. Psychosomatic illness is associated with those patients who most frequently attend medical clinics(59). The medical and human costs of repeated and unrevealing evaluations are astronomical, including the direct cost of diagnostic

evaluations in clinics, emergency rooms and intensive care units, often involving repeated MRIs studies, extensive EEG monitoring, epileptic drug (AED) prescriptions (60), and other inappropriate treatments (61). Missed work and the emotional toll on concerned family members constitute additional expenses that are difficult to quantify but potentially avoidable with improved diagnosis and treatment.

II. Specific Aims:

Primary Aim and Hypotheses

The primary goal of this study is to provide objective measures of neural circuit activity that can clarify the neurobiology of motor-related FND, using advanced MRI techniques. In addition, psychological variables are also assessed to determine differences between FND and healthy subjects as well as compare differences across FND subtypes.

Specific Aim 1: SA1) To examine resting-state functional connectivity patterns and correlations with measures of interest in patients with motor-related FND compared to healthy subjects.

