Hypotheses: Compared to healthy subjects, PNES, FMD and functional weakness related FND subtypes will demonstrate diminished rs-FC between the orbitofrontal cortex(OFC), anterior cingulate cortex(ACC) and the amygdala. rs-FC will also be abnormal across emotional processing, attentional and motor control networks in patients with motor-related FND compared to healthy subjects.

Secondary Aims and Hypotheses:

SA2) To examine volumetric differences between motor-related FND (e.g. PNES, FMD, functional weakness) and healthy subjects.

Hypotheses: FND patients will demonstrate structural alterations in limbic-paralimbic, attentional and motor related brain regions.

SA3) To examine psychometric differences between FND and healthy subjects, as well as compare differences between PNES, FMD, and functional weakness patients.

Hypotheses: FND patients will demonstrate increase anxiety, depression, dissociation and decreased resilience to stress compared to healthy subjects. PNES patients compared to other patient groups will report more extensive dissociative and psychological trauma based symptoms.

III. Subject Selection

a. Inclusion/exclusion criteria:

Inclusion criteria: FND patients of several distinct subtypes will be recruited including: 120 PNES subjects diagnosed by vEEG and/or clinical criteria(62), 120 FMD subjects meeting established clinical diagnostic criteria(63, 64), 120 patients with functional weakness diagnosed by “positive” signs suggestive of functional weakness including but not limited to a positive Hoover’s sign, and 120 healthy subjects will be recruited. Of note, patients with PNES or FMD will be recruited to include individuals who are clinically suspected to have PNES or FMD. Additionally, 60 patients with other somatoform symptoms and 60 patients with depression (major depression, dysthymia or depression NOS) will be recruited as patient control groups. Individuals between the ages of 18 and 99 will be offered the potential for study participation.

Exclusion criteria: Any significant major neurological disorder resulting in specific MRI abnormalities (i.e. encephalomalacia, severe traumatic brain injury (TBI)), poorly controlled major medical illness with known central nervous system consequences, inability to read English, pregnancy, claustrophobia, or inability to satisfy MRI safety measures.

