The self-report psychometrics collect data on variables such as impulsivity, depression dissociation, psychological trauma, resilience, personality, somatization, attachment, pain catastrophizing, reading ability, handedness and participant specific FND characteristics. Clinician administered psychometrics provide evidence for co-morbid psychiatric conditions while our focused chart review will help collect subject specific FND characteristics, risk factor qualification, review of prior diagnostic evaluations, and review of prior and current treatment strategies. Blood Oxygenation Level-Dependent contrast is measured during functional imaging to reflect changes in venous deoxyhemoglobin associated with neuronal activity. Volumetric quantification will be obtained from SPGR images and white matter tracts will be delineated using diffusion tensor imaging.

b. Study Endpoints

Study endpoint is recruitment of enough participants to comply with our power analysis (30 for each subject group).

c. Statistical Methods**Regions of Interest:****Functional Connectivity Analyses:**

Functional connectivity analyses will be performed using region of interest (seed-based) and whole brain data driven approaches(72-74). Correlational analyses will also be performed to assess associations between connectivity patterns and psychometric measures of interest.

Volumetric Analyses:

High-resolution T1-MRI images will be analyzed using semi-automated quantitative techniques such as voxel-based morphometry(15) and cortical thickness analyses(14, 75). Correlational analyses will also be performed to assess associations between volumetric patterns and psychometric measures of interest.

d. Power Analysis:

Based on neuroimaging studies in other neuropsychiatric populations(24, 76, 77), it is estimated that regions-of-interest will have a mean BOLD signal group difference of 0.7 with a standard deviation of 0.95. For a power of 0.8, approximately 60 total subjects would be needed. We are now adding plans for study replication which will include the need for 60 subjects in each additional study arm. Given that comparisons may include FND vs. Healthy subjects (30 in each group) as well as comparisons between PNES vs. Healthy Subjects, FMD vs. Healthy Subjects, and Functional Weakness Patients vs. Healthy Subjects a total of 30 subjects in each patient group and healthy subject group will be recruited.

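### The stated power of 0.8 covers one mean-BOLD contrast at 30 v 30, not the connectivity aim SA1, and the group size is 30 in VI.b and VI.d but 120 in III.a

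*Combined protocol and SAP*

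**What the plan says.** **Aim.** Section II makes SA1 the primary aim: "To examine resting-state functional connectivity patterns and correlations with measures of interest in patients with motor-related FND compared to healthy subjects". Its hypotheses predict reduced connectivity among orbitofrontal cortex, anterior cingulate and amygdala in PNES, FMD and functional weakness, plus abnormal connectivity across wider networks.

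**Analysis.** VI.c plans seed-based and whole-brain connectivity analyses, plus correlations with psychometric measures. It names no primary connection, significance level, multiplicity method or rule for what counts as support.

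**Power.** VI.d takes its inputs from studies in other neuropsychiatric populations: "it is estimated that regions-of-interest will have a mean BOLD signal group difference of 0.7 with a standard deviation of 0.95". It concludes: "For a power of 0.8, approximately 60 total subjects would be needed". It then lists pooled FND and each of the three subtypes against healthy subjects, opening with "Given that comparisons may include FND vs. Healthy subjects (30 in each group".

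**Group size.**
- VI.d: "a total of 30 subjects in each patient group and healthy subject group will be recruited".
- VI.b: "Study endpoint is recruitment of enough participants to comply with our power analysis (30 for each subject group".
- III.a: 120 in each of the three FND subtypes, and "120 healthy subjects will be recruited". It adds two patient control groups of 60 (other somatoform symptoms; depression).
- VI.d also says: "We are now adding plans for study replication which will include the need for 60 subjects in each additional study arm".

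**The concern.** A reader of VI.d would take it that the primary aim has 0.8 power at 30 per group. The calculation does not show this. It concerns a different measure and a single two-group test, while SA1 has several contrasts that share one healthy group. Without a decision rule, neither the false-positive rate nor the power of SA1 can be stated.

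The conflicting sizes make this harder to judge. Taken literally, VI.b ends recruitment at a quarter of the III.a target (30/120), and the difference between 30 and 120 decides how small a connectivity difference the study can detect.

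**Working it through.** **1. Reproducing the plan's figure.** Inputs from VI.d: difference 0.7, SD 0.95, power 0.8, equal groups. Two-sided 0.05 is my assumption.

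- d = 0.7/0.95 = 0.737.
- Normal approximation: n = 2(1.960 + 0.842)²/0.737² = 28.9, so 29 per group and 58 in total.
- Two-sample t-test: n = 29.9, so 30 per group and 60 in total. Power at 30 v 30 is 0.801.
- One-sided 0.05 would need only 46 (normal) or 48 (t) in total, so two-sided 0.05 is the level that fits the stated 60.

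The arithmetic is right for one mean-BOLD contrast.

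**2. Does it cover SA1?** The input is a mean regional BOLD difference. SA1 is about connectivity between regions. The documents give no connectivity difference or SD, so 0.8 cannot be carried across without a further assumption.

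**3. Pooled FND v healthy.** Three groups of 30 pool to 90, not 30. At 90 v 30, on the BOLD inputs, power is 0.93. The pooled number is smaller if patients belong to two subtypes. The event-log entry in V.e allows for this, and no rule assigns such patients.

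**4. False positives at 30 per group, one connection, non-overlapping subtypes, no true difference.** Three independent tests would give 1 − 0.95³ = 14.3%. Sharing the healthy group correlates the contrasts at about 0.5, so I simulated it (200,000 runs):

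| Testing scheme | Chance of at least one false positive |
|---|---|
| Three subtype contrasts, each at two-sided 0.05 | about 12.5% |
| Same, counting only the predicted direction | about 6.3% |
| Three subtypes plus pooled, each at two-sided 0.05 | about 13% |
| Holm over three subtypes, pooled unadjusted at 0.05 | just under 7% |
| Holm over all four | roughly 3.5% |

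Holm over the subtypes alone is therefore not enough if the pooled contrast is also tested at 0.05.

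**5. Joint power, if d = 0.737 carried over to connectivity.** Each subtype contrast at 0.05 has 0.80 at 30 per group. All three succeeding together has about 0.61 at 30, 0.95 at 60 and above 0.99 at 120.

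**6. Smallest standardised difference detectable with 0.8 power, per subtype contrast, one connection.**

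| Level | 30 per group | 60 per group | 120 per group |
|---|---|---|---|
| 0.05 | 0.74 | 0.52 | 0.36 |
| 0.05/3 | 0.86 | 0.60 | 0.42 |
| 0.05/4 | 0.89 | 0.62 | 0.43 |

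The three named regions form three pairs. Three connections by three subtypes is nine tests. At 0.05/9 and an assumed d of 0.5, power per test is 0.18, 0.47 and 0.86 at 30, 60 and 120 per group. None of these figures applies to the whole-brain analyses.

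**The case against.** The strongest defence is that VI.d makes no arithmetic error and no claim of joint power. It powers a two-group difference and says which comparisons may follow. On its own inputs each subtype contrast does have 0.80 at 30 v 30. The study is non-interventional, its aims are to examine, and section II does not say that all three subtypes must succeed. This stands, and it limits the point. Three stronger readings are tempting:

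- *Three rival group sizes.* The 60 per additional arm could be a third value for the same groups. The sentence mentions replication, but it also fits the two 60-patient control groups in III.a. It is ambiguous and not a firm conflict. The replication reading (30 + 30) does not produce 120 either.
- *True power is 0.61, not 0.80.* This holds only under an all-three rule, which the plan never states.
- *False support for SA1 runs at 12.5%.* That rate is two-sided. The subtype hypothesis is directional, and the rate in its direction is about 6.3%.

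It could also be said that 120 per group makes power ample. For one connection with the BOLD-based effect it does. With nine tests and d = 0.5 it is 0.86, and less if replication splits the groups.

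An exploratory purpose does not dispose of the point. Section II names SA1 as primary with a directional, region-specific hypothesis, and VI.d claims a power. The wrong measure and the missing rule remain at any group size.

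**Conclusion.** Wrong as written, in two respects.

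First, 30 and 120 are both given in current text as the recruitment for the same FND and healthy groups, and VI.b makes 30 the study endpoint. These cannot both hold.

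Second, the 0.8 is correct for one mean-BOLD contrast at 30 v 30 but is not a power statement for SA1. It lacks a connectivity effect, a significance level, a decision rule and error control over the four listed contrasts. Uncorrected, the chance of at least one false positive is about 12.5% for the three subtypes (about 6.3% in the predicted direction) and about 13% with the pooled contrast added. The 30-per-group description of the pooled contrast also does not match up to 90 v 30.

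The error rates assume one connection, non-overlapping subtypes and a 0.05 level inferred from the stated sample size. Any power for SA1 also assumes an effect size that the documents do not give.

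**What to change.** 1. **Group size.** Reconcile 30 and 120 for the FND subtypes and the healthy group across III.a, VI.b and VI.d. Say what the 60 per additional arm refers to and how replication divides the n. Give the true allocation for pooled FND v healthy, with a rule for patients who have more than one subtype. The two control groups of 60 may keep their own size.

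2. **Decision rule.** State two-sided alpha 0.05, name the primary connection(s), and choose one rule for SA1:
   - pooled FND v healthy as the single primary contrast at 0.05, with the subtypes tested after it by Holm;
   - Holm over all four contrasts, if any one counts as support; or
   - each contrast at 0.05, if all are required.

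   Extend the family if more than one connection is primary.

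3. **Power.** Replace the mean-BOLD statement with power conditional on an assumed standardised connectivity difference, marked as an assumption, at the adopted n and rule. Alternatively, quote the detectable differences in the table above.

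The cost is wording in II, III.a and VI, and a less favourable stated power if 30 per group is kept. No recruitment beyond the targets already stated is needed.

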During the initial communication, the researcher will describe the nature of the study to the patient (i.e. psychologic assessment, focused chart review, MRI based brain imaging, follow-up questionnaire assessments) and verify eligibility based on our inclusion and exclusion criteria (see attached phone script). If appropriate, the researcher will then schedule a date and time for subject to present in person to provide informed consent and begin study participation.

Control subjects once identified by our recruitment methods will likewise be contact by phone to describe the nature of the study (i.e. psychologic assessment, MRI based brain imaging) and verify eligibility based on our inclusion and exclusion criteria (see attached phone script) prior to scheduling a date and time for participant to present in person to provide consent and begin study participation.

All subjects will visit MGH on up to five instances based on subject participation preference for the following activities:

Depending on researcher availability, subjects may also be given the opportunity to complete structured clinical interviews either at the end of session 2 or via telephone if completion as part of session one is not possible. Healthy control subjects may be given the option of completing REDCAP based questionnaire via an emailed link or to complete all questionnaires on the same day as the brain scan. FND subjects participating in follow-up sessions may be given the option of completing REDCAP-based questionnaires via an emailed link. This option will only be offered to subjects who are deemed by a study doctor to pose minimal risk of mental health symptoms requiring immediate evaluation or monitoring. This specific data capture method is being used to enable the capture of follow-up data in patients whom have improved to the point that they are no longer being followed longitudinally in clinic or for those individuals whom for other reasons (i.e. geography) are not being followed longitudinally clinically but are interested in participating in longitudinal aspects of the research study. Whenever possible, follow-up visits will take place in-person.

1. Informed consent to explain the study and for access to relevant medical records, and permission to contact for future possible follow-up studies.
2. Completion of structured clinical interviews and self-report psychological questionnaires
3. Brief day of scanner psychological assessments and MRI based brain scanning.

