4. Follow-up clinical and psychological questionnaires at approximately 6 months, 12 months, and 24 months (FND Subjects Only).

Subjects may participate in this study for a maximum of 8-9 hours for the initial assessment (1-3). If subjects, elect to participate in the follow-up questionnaires, an additional approximately 2 hours of participation is expected for each session. Subjects participating as healthy volunteers will complete an abbreviated set of self-report questionnaires (2), and may participate in this study for a maximum of 6 hours for the initial assessment (1-3).

b. Method for obtaining informed consent:

Written informed consent will be obtained from the patient or normal subject prior to his/her participation. Consent will be obtained by designated laboratory members with prior explicit training in consent administration. The consent form will be discussed in detail with the subject; the form will be reviewed item by item to ensure an understanding of the purposes and potential risks of the study, including its investigational nature. Subjects will be allowed to read and review the consent in full at their leisure before agreeing to participate. Only patients capable of giving informed consent will be studied.

As noted, participants will complete most psychologic assessments on a separate day from MRI scanning (see detailed list below).

Subjects will be reimbursed 50 dollars for their participation in our detailed psychologic assessment and 50 dollars for participation in our neuroimaging study with brief additional psychologic assessment. Subjects will also be reimbursed an additional 25 dollars for participation in each follow-up assessment. Subjects will also be reimbursed for parking via a parking voucher at both the MGH main campus and the Charlestown sites.

c. Treatment assignment and randomization:

This segment is not applicable to our study because no treatment is offered.

V. Study Procedures

a. Study visits and parameters to be measured:

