Participants will visit MGH up to five times. During the initial visit, informed consent will be obtained. Participants will also provide consent for a focused review of their medical records pertaining to the diagnosis of FND (i.e. admission and progress notes, EEG reports, neuroimaging reports, neuropsychological assessments and consult or service notes from Psychiatry, Neurology, Psychology and Social Work). We will also ask consent to review hospital records on current and prior medication use and for permission to contact them in the event of future follow-up research studies. Subjects may decline future follow-up contact. Following consent, all eligible participants will either be administered a clinical interview and a battery of self-report measures or participate in the resonance imaging paradigm with associated brief psychologic and cognitive assessments. The order of study participation will be determined by scanner availability and/or participant and investigator preference.

Subjects unable to participate in the MRI portion of the study for any reason, may still be offered the opportunity to participate in the clinical interview, self-report questionnaire and review of medical records portion of the study.

During the neuroimaging portions, data will be collected during the resting state. Structural measures will also be acquired.

Depending on subject and investigator availability, healthy control subjects only may be given the opportunity to complete secure web-based questionnaires through an emailed link. In addition, structured

clinical interviews and the full battery of questionnaires may be performed at the end of session 2 or offered via telephone depending on researcher availability.

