Beck Depression Inventory

Dissociative Experience Scale

Somatoform Dissociation Questionnaire-20

SF-36v1 Healthy Survey

Screening for Somatoform Symptoms-Conversion Subscale

Screening for Additional Somatoform Symptoms

Event Log (for FND subjects with PNES and/or those with other paroxysmal functional motor symptoms)

Please note, either paper and pencil or REDCAP administered versions of the psychometrics will be used for all psychometric data collection. The opportunity will also be made available for healthy control subjects only to potentially complete REDCAP based psychometrics via an secure emailed link. Note, patients with depression will not participate in the follow-up portions of this study at 6, 12 and 24 months.

Also, subjects who have completed the above psychometrics for related studies by collaborators in close temporal proximity to our study may potentially not complete redundant psychometric but rather may have their data taken from those closely related studies. Questionnaires that were not completed during the baseline visit may be offered at follow-up.

Image Acquisition:

Functional imaging: BOLD contrast imaging, which reflects changes in venous deoxyhemoglobin associated with neuronal activity, will be used.

Rest Task Procedure:

The rest tasks will be acquired over 1-4 scanning sessions each up to 10 minutes while individuals are at rest.

Structural imaging: A high-resolution T1 weighted anatomical image will be acquired. In addition, diffusion tensor imaging acquisition sequences will also be acquired.

VI. Biostatistical Analysis**a. Specific data variables being collected for the study:**

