VII. Risks and Discomforts**a. Complications of surgical and non-surgical procedures:****Risk of clinical exacerbation:**

During psychologic assessment participants will be asked potentially sensitive and stressful information about themselves. Subjects will be made aware of this psychologic investigation both in the recruitment phase of the study and more explicitly during the consent process.

In the event that participants are found to have psychopathology requiring immediate psychiatric evaluation, such as that which entails potentially imminent risk of harm to self or others, they will be escorted to the Emergency Room for clinical evaluation and treatment. In cases where the presence of such psychopathology is unclear, the research physician will assess the participant/situation to determine whether immediate clinical psychiatric evaluation is required (in which case the participant would be escorted to the emergency room). If acute evaluation is not found to be necessary, but follow up monitoring and evaluation is advisable, this will be discussed with the participant, and the participant's primary care physician or physician primarily involved in care will be notified. To protect against forced disclosure of sensitive participant information, participants are asked to complete a certificate of confidentiality consent form.

For subjects who participate remotely for any follow-up session, a study doctor will be available to answer questions and address any concerns. The study doctor will selectively review questionnaire responses when the session is complete to determine whether these indicate mental health symptoms requiring immediate psychiatric evaluation. More specifically, item 9 of the Beck Depression Inventory will be reviewed to evaluate if a research subject has endorsed any suicidality. For a score of 1 or above, the study doctor will contact the subject by phone for an additional phone triage regarding any concern and if necessary will also notify the participant's physician.

Risk of uncovering structural brain pathology.

The pulse sequences used in these experiments are not those used for clinical diagnostic studies and are therefore not geared toward looking for structural pathology. If an abnormality is noted on the scans that are obtained, the patient and patient's physician will be notified.

Pregnant subjects:

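### The remote-session suicidality check in VII.a is worded for follow-up only, so healthy controls who answer the Beck inventory by emailed link at baseline fall outside its stated scope

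*Combined protocol and SAP*

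**What the plan says.** Section VII.a (Risk of clinical exacerbation) has a paragraph on remote participation. It begins "For subjects who participate remotely for any follow-up session, a study doctor will be available to answer questions and address any concerns". It continues "The study doctor will selectively review questionnaire responses when the session is complete", then specifies that "item 9 of the Beck Depression Inventory will be reviewed to evaluate if a research subject has endorsed any suicidality", and gives the trigger: "For a score of 1 or above, the study doctor will contact the subject by phone". No other section mentions a review of item 9.

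Follow-up is restricted in IV.a, item 4: "Follow-up clinical and psychological questionnaires at approximately 6 months, 12 months, and 24 months (FND Subjects Only").

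Three sections offer healthy controls a remote route:

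- IV.a: "Healthy control subjects may be given the option of completing REDCAP based questionnaire via an emailed link". The stated alternative is to do everything on the day of the scan.
- V.a: "healthy control subjects only may be given the opportunity to complete secure web-based questionnaires through an emailed link".
- V.e: "The opportunity will also be made available for healthy control subjects only to potentially complete REDCAP based psychometrics via an secure emailed link".

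V.e lists the baseline self-report measures. Those that healthy volunteers skip carry an explicit note, for example the Barratt scale. The Beck Depression Inventory carries none.

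**The concern.** The protocol asks healthy volunteers a suicidality question and allows them to answer it off site. It then describes who reads such answers, and what happens next, only for a type of session that these volunteers never have. Followed to the letter, the plan instructs nobody to look at item 9 on a healthy control's remote baseline form.

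Being in the healthy group does not by itself remove the issue. The exclusion criteria in III.a contain no psychiatric criterion, and III.b recruits controls by advertisement, so a referring clinician cannot be assumed. What is at stake is participant safety. No estimate or test is affected.

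**Working it through.** The protocol gives no figure to reproduce. The check is a reading of the sections side by side.

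1. **Scope of the review.** In VII.a, study-doctor availability, the review of responses, the item 9 check and the call at a score of 1 or above form one paragraph, introduced by a sentence about remote follow-up sessions.

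2. **Who has follow-up.** IV.a limits it to FND subjects. V.a offers it to FND subjects, and V.e adds that patients with depression do not take part. A healthy control has none.

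3. **Who completes the Beck inventory at baseline.** V.e marks its exemptions individually and the Beck inventory is not among them, so healthy controls complete it.

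4. **Whether they may do so remotely.** IV.a, V.a and V.e all allow an emailed link. None lists the questionnaires that the link carries. I assume that it includes the Beck inventory, because no measure is excluded and the alternative in IV.a covers all questionnaires.

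5. **Result.** From 2 to 4, a healthy control's remote Beck form is always a baseline form. From 1, it lies outside the stated review. V.a and V.e reserve the control-group link for healthy controls alone, so this is the one group with a remote baseline route.

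6. **Whether another provision fills the gap.**
   - *Minimal-risk screen.* In IV.a it comes directly after the sentence on FND follow-up and is justified by the need for follow-up data in patients. V.a attaches it to FND follow-up. V.a and V.e offer controls the link without it. Even on the wider reading, it decides who receives the link and does not review the answers.
   - *General escalation paragraph in VII.a.* It covers all participants, but it acts once psychopathology is found or its presence is unclear. It names no step that examines remote answers, and its acute action is an escort to the emergency room, which presupposes that the participant is on site.
   - *Structured clinical interview (SCID).* V.e gives it to all eligible participants. IV.a and V.a allow it at the end of session 2 or by telephone. It is not linked to the inventory answers or to when they are entered.
   - *Data checks in IX.b.* These concern data entry, data quality and adherence to the protocol.

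7. **Size.** Number affected = healthy controls recruited × proportion using the link. The target is 120 in III.a and 30 per group in VI.b and VI.d. No proportion is given, so it can lie anywhere from 0 to 1. With 30 controls the range is 0 to 30; with 120 it is 0 to 120. The stated review covers 0 of them in either case.

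**The case against.** The best reply is that the plan already looks for psychopathology in controls at baseline, so a special rule is needed only for remote follow-up. The SCID exemption argument fails for a critic: V.e exempts healthy volunteers from the two cognitive and reading tests beside it, but not from the SCID itself. Controls also have an eligibility call, in-person consent and a scan-day visit with brief psychological assessment. A patient in remote follow-up may have no such contact, since IV.a and V.a describe people no longer seen in clinic. That explains why VII.a singles out follow-up. This point stands as a reduction of risk. It does not close the gap, because none of these contacts is tied to the remote answers.

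The minimal-risk screen may also cover controls. In IV.a the control link, the FND link and the screen come in consecutive sentences, and the screen refers to subjects in general. That reading is open, though the surrounding text favours the narrower one. The phone script mentioned in IV.a and the consent pages are not in the file, and either might bear on the screening of controls.

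A reader might infer that the sections contradict one another. They do not: a study team can offer the link to controls and apply VII.a to remote follow-up without breaching either. A reader might also infer that suicidality answers will go unread. The documents support only the statement that no review is specified; IX.a also describes continuous oversight by the investigators and coordinator.

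**Conclusion.** The gap is real and confined to scope. VII.a words its item 9 review, study-doctor availability and telephone triage for remote follow-up, and that wording leaves out the remote baseline route offered to healthy controls in three places. Existing safeguards lower the risk without addressing those answers.

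At most 30 to 120 people are concerned, depending on the target. It would be tempting to report 120 as the number exposed, but that is an outer bound: it requires the larger target and use of the link by every control.

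The conclusion assumes that the link carries the Beck inventory and that no document outside the file extends the review. If the minimal-risk screen does apply to controls, the concern is smaller but remains. Because it bears on participant safety it deserves correction, but as a clarification and not as a critical defect. It has no bearing on sample size, endpoints or analysis.

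**What to change.** Reconcile IV.a, V.a, V.e and VII.a on two points:

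- VII.a should state its scope so that the remote-session review matches every remote route the protocol offers for the Beck inventory, including the baseline link for healthy controls.
- IV.a should state whether the minimal-risk screen applies to healthy controls or only to FND subjects at follow-up, and V.a and V.e should agree with it.

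How the scope and the routes are brought into line, and what the clinical rule contains, is for the investigator to decide. The cost is a sentence or so of protocol wording and a small amount of review time, depending on the rule chosen.
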